1. VERSION HISTORY

Version/ Date	Associated Protocol Amendment	Rationale	Specific Changes
1	Original	NA	NA
XX Sep 2019	31 Jul 2019		

2. INTRODUCTION

This statistical analysis plan (SAP) provides the detailed methodology for summary and statistical analyses of the data collected in Study B7461027. This document may modify the plans outlined in the protocol; however, any major modifications of the primary endpoint definition or its analysis will also be reflected in a protocol amendment.

The analyses of this study will include all data up to a data cut-off date after End of Trial, defined as 12 calendar months after the "last patient first visit" (LPFV) date in the study.

All summaries and analyses will include all data pertaining to visits/assessments performed up to and including the data cut-off date.

2.1. Study Objectives, Endpoints, and Estimands

Study B7461027 is a post-authorization efficacy study (PAES) requested by EMA in order to obtain additional data on the activity of lorlatinib for the treatment of patients with ALK-positive metastatic non-small-cell lung cancer whose disease has progressed after alectinib or ceritinib as the first ALK tyrosine kinase inhibitor (TKI) therapy.

The study focuses mainly on evaluation of antitumor activity, with analysis of safety data limited to Adverse Events.

Objectives	Estimands	Endpoints
Primary		
• To assess Overall and Intracranial Response Rate of single-agent lorlatinib in participants with advanced ALK- positive NSCLC whose disease has progressed on alectinib or ceritinib as the first ALK tyrosine kinase inhibitor (TKI) therapy	• The primary estimand is the treatment effect of lorlatinib by independent central review (ICR) from time of first dose until progression is met or subsequent anti-cancer therapy is administered for all participants who receive at least one dose of lorlatinib without regard to discontinuation from treatment; all	Confirmed Objective Tumor Response assessed by Response Evaluation Criteria in Solid Tumor (RECIST) version 1.1 per ICR

DMB02-GSOP-RF02 4.0 Statistical Analysis Plan Template 01-Nov-2018

PFIZER CONFIDENTIAL Page 5

TMF Doc ID: 98.03

	response assessments regardless of gaps in tumor assessments are considered	
Secondary		
 To assess secondary measures of clinical efficacy 	 The estimand for Objective Response (OR) by investigator (INV) follows the estimand specified for the primary endpoint except that the treatment effect is based on INV The estimand for Intracranial (IC) response is the Intracranial treatment effect (ie in brain lesions) of lorlatinib from time of first dose until Intracranial progression is met or subsequent anti-cancer therapy is administered for all participants who receive at least one dose of lorlatinib without regard to discontinuation from treatment; all response assessments regardless of gaps in tumor assessments are considered The estimand for Time to Tumor Response (TTR) is the treatment effect from the time of first dose to the first date of response that is subsequently confirmed for all participant who are responders to lorlatinib 	 Every endpoint assessed by RECIST version 1.1 Confirmed Objective Tumor Response assessed per INV Confirmed Intracranial tumor response assessed per ICR/INV TTR per ICR/INV DOR per ICR/INV Duration of Intracranial response (IC-DOR) per ICR/INV PFS per ICR/INV TTP per ICR/INV

 The estimand for Duration of Response (DOR) is the treatment effect from the first date of OR that is subsequently confirmed for all participant who are responders to lorlatinib until progression or death, without regard to discontinuation from treatment unless new anti-cancer therapy is initiated or extended gap in tumor assessment is present prior to progression or death The estimand for IC-DOR follows the estimand specified for the DOR, but limited to intracranial lesions 	
 The estimand for Progression Free Survival (PFS) is the treatment effect from the time of first dose for all participants who receive at least one dose of lorlatinib until progression or death, without regard to discontinuation from treatment unless new anti- cancer therapy is initiated or an extended gap in tumor assessment is present prior to progression or death 	
• The estimand for Time to Tumor Progression (TTP) is the treatment effect from the time of first dose	

DMB02-GSOP-RF02 4.0 Statistical Analysis Plan Template 01-Nov-2018 PFIZER CONFIDENTIAL Page 7 TMF Doc ID: 98.03

	for all participants who receive at least one dose of lorlatinib until progression, without regard to discontinuation from treatment unless participant dies, new anti- cancer therapy is initiated or extended gap in tumor assessment is present prior to progression	
• To confirm the safety and tolerability of lorlatinib	• The estimand for safety is the incidence of Adverse Events from the time of first dose to 28 days post last dosing date or the date of initiation of a new anti-cancer therapy for all participants who receive at least one dose of Lorlatinib	• Adverse Events as characterized by type, frequency, severity (as graded by National Cancer Institute Common Terminology Criteria for Adverse Events [NCI CTCAE] v.4.03), seriousness, and relationship to study therapy

2.1.1. Primary Estimand

The primary estimand is the treatment effect of Lorlatinib from the time of first dose until progression is met, death or subsequent anti-cancer therapy is administered regardless of tolerability or duration on treatment. It includes the following 4 attributes:

- Population: Participants with Anaplastic Lymphoma Kinase (ALK)-Positive Non-Small Cell Lung Cancer (NSCLC) Whose Disease Progressed After One Prior Second-Generation ALK Tyrosine Kinase Inhibitor (TKI), as defined by the inclusion and exclusion criteria, and who receive at least one dose of lorlatinib
- Variable: Confirmed Objective Response according to RECIST 1.1 per ICR, defined as CR or PR from the date of first dose until PD, death, or start of new anticancer therapy
- Intercurrent event: All data after the intercurrent event "start of subsequent anticancer therapy treatment" will be excluded; non adherence to treatment is not an intercurrent event; assessments are considered regardless of gaps in assessments
- Population-level summary: ORR, ie percentage of participants with confirmed complete response [CR] or confirmed partial response [PR] and associated exact CI

DMB02-GSOP-RF02 4.0 Statistical Analysis Plan Template 01-Nov-2018 PFIZER CONFIDENTIAL Page 8 TMF Doc ID: 98.03

2.1.2. Secondary Estimands

A secondary estimand is the treatment effect of Lorlatinib from the time of first dose until progression is met, death or subsequent anti-cancer therapy is administered regardless of tolerability or duration on treatment. It includes the following 4 attributes:

- Population: Participants with Anaplastic Lymphoma Kinase (ALK)-Positive Non-Small Cell Lung Cancer (NSCLC) Whose Disease Progressed After One Prior Second-Generation ALK Tyrosine Kinase Inhibitor (TKI), as defined by the inclusion and exclusion criteria, and who receive at least one dose of lorlatinib
- Variable: Confirmed Objective Response according to RECIST 1.1 per INV, defined as PR or CR from the date of first dose until PD, death, or start of new anticancer therapy
- Intercurrent event: All data after the intercurrent event "start of subsequent anticancer therapy treatment" will be excluded; non adherence to treatment is not an intercurrent event; assessments are considered regardless of gaps in assessments
- Population-level summary: ORR, ie percentage of participants with confirmed complete response [CR] or confirmed partial response [PR] and associated exact CI

A secondary estimand is the durability of treatment effect of Lorlatinib from the time of first response until progression is met, death or subsequent anti-cancer therapy is administered regardless of tolerability or duration on treatment for participants showing a confirmed OR per ICR/INV. It includes the following 4 attributes:

- Population: Participants meeting same criteria of Primary estimand and showing a confirmed OR per ICR/INV
- Variables: DoR /DoR censoring status
- Intercurrent event: All data after the intercurrent event "start of subsequent anticancer therapy treatment" will be excluded; non adherence to treatment is not an intercurrent event; assessments are considered regardless of gaps in assessments
- Population-level summary: Kaplan-Meier Median of DOR and associated CI

Another secondary estimand is the intra-cranial treatment effect of Lorlatinib from the time of first dose until intra-cranial progression is met per ICR/INV, death or subsequent anticancer therapy is administered regardless of tolerability or duration on treatment. It includes the following 4 attributes:

• Population: Participants meeting same criteria of Primary estimand and having CNS metastases at study entry

DMB02-GSOP-RF02 4.0 Statistical Analysis Plan Template 01-Nov-2018 PFIZER CONFIDENTIAL Page 9 TMF Doc ID: 98.03

- Variable: Confirmed IC-OR according to RECIST 1.1 per ICR/INV, defined as intra cranial PR or CR from the date of first dose until PD, death, or start of new anticancer therapy
- Intercurrent event: All data after the intercurrent event "start of subsequent anticancer therapy treatment" will be excluded; non adherence to treatment is not an intercurrent event; assessments are considered regardless of gaps in assessments
- Population-level summary: IC-ORR, ie percentage of participants with confirmed intra-cranial complete response [CR] or confirmed intra-cranial partial response [PR] and associated exact CI

Another secondary estimand is the durability of intra-cranial treatment effect of Lorlatinib from the time of first intra-cranial response until intra-cranial progression is met, death or subsequent anti-cancer therapy is administered regardless of tolerability or duration on treatment for participants showing a confirmed IC-OR per ICR/INV. It includes the following 4 attributes:

- Population: Participants meeting same criteria of Primary estimand, having CNS metastases at study entry and showing a confirmed IC-OR per ICR/INV
- Variable: IC-DOR according to RECIST 1.1 per ICR/INV
- Intercurrent event: All data after the intercurrent events "start of subsequent anticancer therapy treatment" or "extended gap in tumor assessment prior to progression or death"; non adherence to treatment is not an intercurrent event; assessments are considered regardless of gaps in assessments
- Population-level summary: Kaplan-Meier Median of IC-DOR and 95% CI

Another secondary estimand is the time to effect of Lorlatinib from the time of first dose until response is met for participants showing a confirmed OR per ICR/INV. It includes the following 4 attributes:

- Population: Participants meeting same criteria of Primary estimand and showing a confirmed OR per ICR/INV
- Variable: Time To Response per ICR/INV
- Intercurrent event: All data after the intercurrent event "start of subsequent anticancer therapy treatment" will be excluded; non adherence to treatment is not an intercurrent event; assessments are considered regardless of gaps in assessments
- Population-level summary: median of TTR observed on participants using descriptive statistics

Another secondary estimand is the treatment effect of Lorlatinib from the time of first dose until progression per ICR/INV or death is observed or subsequent anti-cancer therapy is administered regardless of tolerability or duration on treatment. It includes the following 4 attributes:

- Population: Participants meeting same criteria of Primary estimand
- Variable: PFS /PFS censoring status (per ICR/INV)
- Intercurrent event: All data after the intercurrent events "start of subsequent anticancer therapy treatment" or "extended gap in tumor assessment prior to progression or death" will be excluded; non adherence to treatment is not an intercurrent event
- Population-level summary: Kaplan-Meier Median of PFS and 95% CI

Another secondary estimand is the treatment effect of Lorlatinib from the time of first dose until progression per ICR/INV is observed or subsequent anti-cancer therapy is administered regardless of tolerability or duration on treatment. It includes the following 4 attributes:

- Population: Participants meeting same criteria of Primary estimand
- Variable: TTP /TTP censoring status (per ICR/INV)
- Intercurrent event: All data after the intercurrent events "start of subsequent anticancer therapy treatment" or "extended gap in tumor assessment prior to progression" will be excluded; non adherence to treatment is not an intercurrent event
- Population-level summary: Kaplan-Meier Median of TTP and 95% CI

2.2. Study Design

This is a Phase 4 open-label, multi-center, multi-national, non-randomized, prospective, single arm study of lorlatinib in adult participants with ALK-positive NSCLC who progressed on alectinib or ceritinib as first line of treatment for metastatic disease. Approximately 85 participants will be screened to achieve 70 participants assigned to study intervention.

Participants will take lorlatinib at the approved dose of 100 mg QD. Participants will be treated until disease progression per RECIST 1.1, participant refusal/lost to follow-up, or unacceptable toxicity.

Adult participants with ALK+ NSCLC whose disease progressed after one prior second-generation ALK TKI^a

Lorlatinib 100 mg once daily^b

An independent core imaging laboratory will be used in this study for ICR. All sites will be required to submit images for ICR as soon as they are performed at the site so that imaging scans may be read in real time.

After treatment discontinuation participants will be followed for short term follow-up up to 35 days from discontinuation. No long-term follow up will be collected for the study.

The End of Trial is defined as 12 calendar months after the "last patient first visit" (LPFV) date in the study.

3. ENDPOINTS AND BASELINE VARIABLES: DEFINITIONS AND CONVENTIONS

3.1. Primary Endpoint

3.1.1. Confirmed OR by ICR

Objective Response (OR) based on ICR assessment is defined as complete response (CR) or partial response (PR) according to RECIST v1.1 from date of first dose until documented PD or start of new anti-cancer therapy without regard to discontinuation from treatment. Both CR and PR must be confirmed by repeat assessments performed no less than 4 weeks after the criteria for response are first met.

Participants without a CR or PR or with death prior to first post-baseline assessment, inadequate baseline assessment, new anti-cancer therapy started prior to first post-baseline assessment, and all post-baseline disease assessments missing will be considered as non-responders.

3.2. Secondary Endpoints

3.2.1. Confirmed OR by INV

Defined as OR by ICR but evaluated according to INV.

3.2.2. Confirmed IC-OR by ICR/INV

Intra-Cranial Objective Response (OR) based on ICR/derived investigator assessment is defined as Intra-Cranial complete response (CR) or partial response (PR) according to RECIST v1.1 from date of first dose until documented IC-PD or start of new anti-cancer therapy without regard to discontinuation from treatment. Both IC-CR and IC-PR must be confirmed by repeat assessments performed no less than 4 weeks after the criteria for response are first met.

Participants without IC-CR or IC-PR or death prior to first post-baseline assessment,

DMB02-GSOP-RF02 4.0 Statistical Analysis Plan Template 01-Nov-2018 PFIZER CONFIDENTIAL Page 12 TMF Doc ID: 98.03 inadequate baseline assessment, new anti-cancer therapy started prior to first post-baseline assessment, and all post-baseline disease assessments missing will be considered as non-responders.

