3.4. Baseline Variables

The date of first dose (start date) of study treatment is the earliest date of non-zero dosing of the study drug. The date of last dose of study treatment is the latest date of non-zero dosing of the study drug.

No windowing will be applied when defining baseline, except as noted in Section 5.2.8 for tumor assessments. Any deviations from the protocol specified window will be documented as protocol deviations. A separate definition of adequate baseline will be provided for tumor assessment related efficacy endpoints.

For efficacy analyses and baseline characteristics associated with tumor assessments the last assessment prior to treatment start date will serve as the baseline assessment.

For Adverse Events the last assessment performed on or prior to date of the first dose of study treatment will serve as the baseline assessment. If there are no observations meeting these criteria, then baseline is considered missing.

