5.2.5. Measurable Disease

A patient will be considered to have measurable disease if there is at least one target lesion identified at baseline meeting the following criteria:

- Non lymph node lesions with longest diameter ≥ 10 mm by CT scan,
- Non lymph node lesions with longest diameter ≥ 10 mm caliper measurement by clinical exam,
- CNS lesions with longest diameter ≥5 mm provided by gadolinium contrast enhanced MRI perfomed with contingent slices of 1 mm, or
- Lymph nodes with short axis ≥ 15 mm when assessed by CT.

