5.2.8. Adequate Baseline Tumor Assessment

Adequate baseline is defined using the following criteria:

- All baseline assessments must be within 28 days prior to and including the date of first dose.
- All documented lesions must have non-missing assessments (ie, non missing measurements for target lesions and non missing lesions status at baseline for non-target lesions).
- Measurable disease at baseline (see Section 5.2.5 for the definition of measurable disease)

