6.2.2. Confirmed IC-OR by ICR/INV

IC-OR by ICR

Analysis set: Participants with CNS metastases based on ICR

IC-OR by INV

Analysis set: Participants with CNS metastases based on Investigator Assessment

Analysis methodology:

The IC-OR, based on ICR/INV, will be summarized similar to OR (as described above in section 6.1 and 6.2), in Per Protocol Population Participants with CNS metastases based on ICR/INV. Surgery or radiotherapy of extracranial lesions will not affect the determination of IC-OR.

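### The intracranial response rule borrows a whole-body baseline test, so an extracranial gap can turn a confirmed brain response into a failure

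*SAP*

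**What the plan says.** SAP 3.2.2 defines confirmed IC-OR from intracranial lesions and then lists who fails by rule. Participants with "inadequate baseline assessment, new anti-cancer therapy started prior to first post-baseline assessment, and all post-baseline disease assessments missing will be considered as non-responders". The same list appears for overall response in SAP 3.1.1 and 6.1.1, and for IC-OR by ICR in protocol 9.4.1.

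SAP 3.4 announces the meaning of an adequate baseline: "A separate definition of adequate baseline will be provided for tumor assessment related efficacy endpoints". SAP 5.2.8 supplies it, with three conditions:

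- Timing: "All baseline assessments must be within 28 days prior to and including the date of first dose".
- Completeness: "All documented lesions must have non-missing assessments", covering target and non-target lesions.
- Measurable disease, which SAP 5.2.5 defines per patient: "A patient will be considered to have measurable disease if there is at least one target lesion identified at baseline meeting the following criteria".

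None of the three is limited to the brain, and no intracranial version is given.

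SAP 6.2.2 applies the overall-response method to IC-OR in the CNS-metastases sets and adds one extracranial exemption: "Surgery or radiotherapy of extracranial lesions will not affect the determination of IC-OR". SAP section 4 defines those sets by the presence of a brain lesion at study entry. An adequate baseline is not a condition of membership.

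**The concern.** IC-OR is read from brain lesions, but the baseline test that can overrule it looks at the whole body. A participant whose brain disease was fully documented at baseline and then showed a confirmed response can be scored as a failure for a reason unrelated to the brain. That participant stays in the IC-ORR denominator. Because IC-TTR and IC-DoR (SAP 6.2.4 and 6.2.6) use confirmed intracranial responders only, the participant also drops out of both.

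The intracranial estimand in SAP 2.1.2 gives no ground for this. Its variable is confirmed intracranial response, and the only event after which it excludes data is the start of subsequent anti-cancer therapy. Intracranial response rate is named in the primary objective of a study requested by the regulator, so its derivation should not rest on a rule carried over without adaptation.

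**Working it through.** **1. Which defects trigger the rule.** Take a participant with a brain lesion at entry, a complete in-window brain MRI and a confirmed brain response. Under SAP 5.2.8 the baseline is still inadequate if any of these holds:

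- One documented extracranial lesion has no baseline measurement or status (completeness).
- One extracranial scan is out of the window (timing). The Schedule of Activities allows screening scans up to 28 days before registration, and registration up to 2 days before treatment: 28 + 2 = 30 days. A chest CT 29 or 30 days before first dose can therefore comply with the protocol and fail the SAP, while a later brain MRI passes.
- The reader finds no measurable lesion anywhere (measurability). Inclusion criterion 4 requires a measurable extracranial lesion, but Appendix 5 has the investigator classify lesions at baseline, and the central reader may disagree. With no measurable brain lesion either, the response lost by this route would be an IC-CR.

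**2. Direction.** Let m be the number in the CNS set, x the number with a confirmed brain response and an adequate brain baseline, and k the number of those with an extracranial-only defect.

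- Brain-limited rule: IC-ORR = x/m.
- Literal rule: IC-ORR = (x − k)/m.
- Difference: k/m, never negative. If k = 0 there is no effect.

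There is no upward offset, because a gap in a brain lesion also fails 5.2.8.

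**3. The plan's own figure.** None is given for IC-ORR. The sample-size statement for overall response can be checked with the same exact method: 26/60 = 43.3%, Clopper-Pearson 95% CI 30.59% to 56.76%, so the lower limit exceeds 30% as stated. Inflating 60 for 15% drop-out gives 60/0.85 = 71 or 60 × 1.15 = 69, against the planned 70.

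**4. Size under stated assumptions.** The documents give no m and no k. I assume m from 20 to 42 and set x near two thirds of m. The 66.7% in protocol 2.2 motivates that choice, although it refers only to participants with a measurable brain lesion.

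| m (assumed) | x | x/m (exact 95% CI) | k = 1 | k = 2 | Cost per responder |
|---|---|---|---|---|---|
| 20 | 13 | 65.0% (40.78 to 84.61) | 60.0% | 55.0% | 1/20 = 5.0 points |
| 28 | 19 | 67.9% (47.65 to 84.12) | 64.3% | 60.7% | 1/28 = 3.6 points |
| 42 | 28 | 66.7% (50.45 to 80.43) | 64.3% | 61.9% | 1/42 = 2.4 points |

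If a share q of the CNS set has an extracranial-only defect, independent of brain response, the expected rate is 66.7% × (1 − q): 65.4% at q = 2%, 63.4% at 5%, 60.0% at 10%. At q = 15% it is 56.7%, but that is a deliberately high ceiling, because the plan's 15% allowance covers four reasons together.

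**The case against.** The strongest reply is that a brain-limited baseline was plainly meant. Protocol 9.4.1 describes intracranial response from brain lesions only, SAP 3.2.2 closes the response window at intracranial progression, and SAP 6.2.2 keeps extracranial surgery and radiotherapy out of IC-OR. These passages show intent, but they govern how response and progression are determined and what local treatment does. None speaks to baseline adequacy, and a programmer who looks the term up finds only 5.2.8.

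A reader might infer that every available reading goes wrong: the whole-body one for the reason above, and a fully intracranial one because its measurability condition would fail everyone with only non-measurable brain lesions. The documents do not support that. A third reading limits timing and completeness to the brain and leaves measurability at patient level, as SAP 5.2.5 words it. For a participant who meets inclusion criterion 4 on the reader's assessment, neither harm then arises. The difficulty is that this reading is not written down.

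Three further points stand. The trigger needs CNS disease, a confirmed brain response, a sound brain baseline and a purely extracranial defect in one participant, and the documents give no rate for that combination. Any error is conservative. The shift from one participant is small beside an exact interval about 30 points wide at m = 42 and 44 points wide at m = 20.

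**Conclusion.** The point holds as a defect in the stated rule. Applied literally, SAP 3.2.2 with 5.2.8 can score a confirmed brain response as a failure because of an extracranial gap, and nothing else in the documents repairs this. The effect on IC-ORR is zero or downward: 2.4 to 5.0 points per affected responder for an assumed 42 to 20 CNS participants. The number of affected responders is unknown and may be zero.

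Two stronger conclusions might be drawn and are not supported. First, that IC-ORR will be biased: that requires at least one affected responder, and the documents cannot show one. Second, that the study's success is at risk because intracranial response is in the primary objective: IC-OR is listed as a secondary endpoint without a threshold, and the 30% rule in protocol 9.2 and SAP 5.1.2 concerns overall response only. The change should be made before database lock because it is cheap and removes a choice between readings that can give different IC-ORRs.

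**What to change.** Change the SAP only. Protocol 9.4.1 uses the term for an inadequate baseline without defining it, so no amendment is needed.

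Add to SAP 5.2.8 an intracranial adequate baseline for the intracranial endpoints, derived separately for ICR and for INV:

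- baseline brain imaging within the baseline window; and
- a non-missing measurement or status for every brain lesion documented at baseline.

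State that extracranial lesions are not considered and that a measurable brain lesion is not required. Cite this definition in 3.2.2 and 6.2.2. It should also govern IC-DoR, which borrows the PFS censoring rules (SAP 6.2.6). Otherwise a participant restored as a responder would meet the PFS row that censors an inadequate baseline at first dose, before the response began.

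Cost: one extra derived flag and no new data. A footnote is needed, because a participant may be adequate for IC-OR but not for OR. The change does not settle the separate mismatch between the registration anchor in the Schedule of Activities and the first-dose anchor in the SAP: a brain MRI taken 29 or 30 days before first dose would still be out of the window.
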